Study Protocol and Statistical Analysis Plan

1. Data Source

This study utilized data from Taiwan's National Health Insurance (NHI) program, a universal health system established in 1996 that covers over 99% of the population. The claims database provides comprehensive and validated medical records for research use. All personal identifiers were encrypted to protect patient privacy. The study protocol was approved by the Institutional Review Board and conducted in accordance with the Declaration of Helsinki.

2. Study Design

A **nested retrospective cohort design** was adopted to evaluate the association between influenza vaccination (IV) and clinical outcomes following fracture-related hospitalizations.

From the nationwide NHI cohort of more than 23 million insured individuals, we identified **561,566 patients aged ≥65 years** admitted for fracture treatment between 2009 and 2020. Among them, **213,381** received IV within 12 months prior to admission, while **348,185** had not.

To reduce confounding, **1:1 propensity score matching (PSM)** was performed between vaccinated and nonvaccinated patients. Matching variables included:

- Demographics: age, sex
- Socioeconomic status (low-income vs. non-low-income)
- Fracture type and comorbidities (within 24 months)
- Emergency visits and hospitalizations during the prior year

3. Outcomes

The **primary outcomes**, assessed within 30 days postadmission, included:

- Pneumonia
- Septicemia
- Urinary tract infection
- Intensive care use
- Hospital length of stay
- Total medical expenditure
- 30-day mortality

Postfracture infections were identified by physician-coded diagnoses during hospitalization or subsequent claims. Patients with pneumonia or septicemia within 6 months before the fracture were excluded.

4. Measures and Definitions

- **Socioeconomic status:** categorized as low-income or non-low-income per NHI copayment exemption criteria.

- **Comorbidities:** identified from 24-month pre-fracture claims using *ICD-9-CM* codes.
- **Postfracture infections:** defined by ICD-9-CM diagnostic codes (listed in Table S1).
- **Influenza vaccine types:** summarized in Table S2.

5. Statistical Analysis

Propensity scores were estimated using **multivariable logistic regression**, including clinically relevant covariates (Table 1). Matching was performed via a **greedy algorithm** with a caliper width of 0.2 SD of the logit of the propensity score.

- **Categorical variables:** summarized as counts and percentages; compared using the *chi-square test*.
- **Continuous variables:** expressed as mean \pm SD; compared using *independent t-tests*.
- **Risk estimation:** Adjusted odds ratios (ORs) with 95% confidence intervals (CIs) were derived from logistic regression to assess IV effects on infections and mortality.
- **Sensitivity analyses:** stratified by age, sex, comorbidity burden, and fracture type.

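### Twelve admission years are pooled, but admission year is not named among the matching, outcome-model or sensitivity variables, so time trends could pass for a vaccine effect, chiefly on expenditure and length of stay

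*Combined protocol and SAP*

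**What the plan says.** Section 2 (Study Design) defines the cohort as "561,566 patients aged ≥65 years" who were "admitted for fracture treatment between 2009 and 2020". Of these, 213,381 were vaccinated in the 12 months before admission and 348,185 were not.

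The 1:1 matching variables listed there are age, sex, low-income status, fracture type, comorbidities, and "Emergency visits and hospitalizations during the prior year". The last item is a look-back from each patient's own admission, so it does not identify calendar year. The list is introduced as what the variables included, so it may not be complete.

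Section 5 (Statistical Analysis) says the propensity model was fitted "including clinically relevant covariates (Table 1"), and Table 1 is not in the supplied text. The caliper applies to the score alone, and no exact matching is mentioned. Three later steps bear on this point:

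- Adjusted odds ratios are "derived from logistic regression to assess IV effects on infections and mortality". Their covariates are not listed.
- Continuous variables are compared by independent t-tests. Two of the primary outcomes in Section 3 are continuous: length of stay and "Total medical expenditure".
- Sensitivity analyses are "stratified by age, sex, comorbidity burden, and fracture type".

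Admission year, influenza season and price year are named nowhere.

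**The concern.** Over a window of 12 calendar years, vaccine uptake, hospital prices, length of stay and infection risk may all change. If uptake changes, the vaccinated group comes disproportionately from some years. If an outcome also changes, the groups differ on it for reasons unrelated to the vaccine. Matching on patient characteristics does not remove this unless year is in the score or is matched directly.

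The plan offers no clear later repair. For expenditure and length of stay, the match is the only stated control for confounding. Intensive care use is a primary outcome with no stated adjusted model either. For infections and mortality an adjusted model exists, but whether it contains year cannot be told.

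The sample size makes this matter more. With up to 213,381 pairs, a difference of 1% in mean cost gives z of about 3.3 when the coefficient of variation (CV) is 1, and about 1.6 when it is 2. A small time artefact could therefore be reported as a definite saving or a definite extra cost.

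**Working it through.** **1. Stated figures.** 213,381 + 348,185 = 561,566, which matches the cohort total. Overall uptake is 213,381/561,566 = 38.0%. There are 348,185/213,381 = 1.63 unvaccinated patients per vaccinated patient.

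**2. Assumptions (none is in the documents).**
- Admissions are equal in each of 12 years, t = 0 to 11.
- Uptake u_t moves linearly around 38%, over 34–42%, 30–46% or 25–51%.
- The vaccine has no effect, and year is not balanced by the match.
- The number of pairs n is the maximum, 213,381.

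**3. Year mix.** Vaccinated patients have yearly weights w1_t = u_t/Σu_t. Unvaccinated patients have w0_t = (1−u_t)/Σ(1−u_t). If pairing ignores year, and year is unrelated to the matched covariates, the share of same-year pairs is Σ w1_t·w0_t = 8.1–8.3%. About 92% of pairs would then join different years.

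**4. Expenditure growing at rate g a year.** The spurious ratio is R = Σw1_t(1+g)^t / Σw0_t(1+g)^t. Its test statistic is z = ln R / (CV·√(2/n)), with √(2/213,381) = 0.00306. For 34–42% uptake and g = 2%, R = 1.1227/1.1146 = 1.0073, and z = ln(1.0073)/0.00306 = 2.4 at CV 1.

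| Uptake | g | R | z, CV 1 | z, CV 2 |
|---|---|---|---|---|
| 34–42% | 2% | 1.0073 | 2.4 | 1.2 |
| 34–42% | 4% | 1.0145 | 4.7 | 2.3 |
| 30–46% | 2% | 1.0146 | 4.7 | 2.4 |
| 30–46% | 4% | 1.0291 | 9.4 | 4.7 |
| 25–51% | 2% | 1.0239 | 7.7 | 3.8 |
| 25–51% | 4% | 1.0476 | 15.2 | 7.6 |

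Flat uptake gives R = 1.000. A smaller drift of 5 percentage points with g = 2% gives R = 1.0046, with z = 1.5 at CV 1 and 0.7 at CV 2.

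**5. Length of stay falling by a fraction f over the window.** The yearly mean is proportional to 1 − f·t/11, with f = 10%, 20% or 30%. Across the three uptake drifts, R runs from 0.9965 to 0.962, a spurious difference of −0.35% to −3.8%. At CV 1, |z| exceeds 1.96 in 8 of 9 scenarios (range 1.1 to 12.6). At CV 2 it does so in 4 of 9.

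**6. Binary outcome.** The yearly risk is p_t = 0.04(1 − f·t/11). P1 and P0 are its means under w1 and w0. The odds ratio is OR = [P1/(1−P1)]/[P0/(1−P0)], and z = ln OR / √{[1/P1 + 1/(1−P1) + 1/P0 + 1/(1−P0)]/n}. Entries are OR (z).

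| Uptake | f = 10% | 20% | 30% | 50% |
|---|---|---|---|---|
| 34–42% | 0.996 (−0.2) | 0.992 (−0.5) | 0.988 (−0.7) | 0.977 (−1.3) |
| 30–46% | 0.993 (−0.5) | 0.985 (−0.9) | 0.976 (−1.4) | 0.955 (−2.6) |
| 25–51% | 0.988 (−0.7) | 0.975 (−1.5) | 0.961 (−2.4) | 0.927 (−4.2) |

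Nine of 12 scenarios stay below |z| = 1.96. If uptake moves the other way, the spurious ORs are 1.004–1.08.

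**7. Pairs lost to exact year matching.** With 561,566/12 admissions a year, the loss is the sum over years of max(0, vaccinated − unvaccinated). This is 0 for 34–42% (lowest yearly ratio 1.38 unvaccinated per vaccinated), 0 for 30–46% (lowest 1.17), and 936 for 25–51%. The last is 936/213,381 = 0.4%, before calipers.

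**The case against.** The strongest reply is that the covariate set sits in a table not in the supplied text. The listed variables may be incomplete, so year may already be in the score. That stands, and it is why the first request is only to say what Table 1 holds. The pointer to clinically relevant covariates does not settle it, since calendar year is not obviously a clinical covariate.

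It is also fair to say that four of the seven primary outcomes (pneumonia, septicemia, urinary tract infection and 30-day mortality) have an adjusted model with unlisted covariates. Year is unspecified there, not omitted, and in the illustration only steep trends reach significance for such outcomes.

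The size is wholly assumed, and the chosen drifts matter. Smaller drifts, a larger CV or fewer matched pairs all weaken the result, as the 5-point scenario and the CV 2 results show. Drift that is not one-directional can nearly cancel: a symmetric V-shaped uptake between 35.3% and 40.7% gives R = 1.0002 at 2% growth and 1.0006 at 4%. The top of the expenditure range needs uptake to double alongside 4% annual growth. These points limit what the illustration can show. They do not supply the missing control, because the documents give no yearly figures that would rule the bias out.

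The missing adjusted model for intensive care use, the unlisted outcome-model covariates and the reliance on t-tests are gaps in their own right. They matter here only because they leave no clear second line of control for year.

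**Conclusion.** The concern holds, conditionally. Admission year is not named at any step of the analysis, and for expenditure and length of stay no later step would correct its omission from the match. Bias arises only if both uptake and the outcome trend over the window. The documents allow neither its size nor its direction to be determined.

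Under the labelled drifts of 8 to 26 points, the artefact is 0.7–4.8% for expenditure and 0.35–3.8% for length of stay. For a binary outcome starting at 4% risk, the null odds ratio lies between 0.93 and 1.08. Significance depends on the CV and on how many pairs survive the caliper. The point should be fixed, with medium confidence, chiefly for expenditure and length of stay.

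**What to change.** State whether Table 1 contains admission year. If it does, one sentence closes the point.

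If it does not:
- match exactly on admission year, or enter year indicators in the propensity model;
- report post-match balance on year;
- compare expenditure within year-matched pairs or in constant prices, and in the latter case state the price year.

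Month or season is an optional addition, since every admission already has a full 12-month exposure look-back.

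The cost is a re-run of the score and the match, using an admission date that the exposure window and the 30-day outcomes already require. Under the assumed drifts, exact year matching loses at most about 0.4% of pairs on counts, before calipers.

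### Admission season is not a stated restriction, matching variable or stratum, so each 30-day OR averages over high- and low-influenza admissions and cannot show whether the association follows influenza circulation

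*Combined protocol and SAP*

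**What the plan says.** All references are to the combined protocol and SAP.

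- **Section 2, Study Design.** The cohort is "561,566 patients aged ≥65 years", "admitted for fracture treatment between 2009 and 2020". No calendar month or influenza season is named. A patient counts as exposed if he or she "received IV within 12 months prior to admission". The listed matching variables are age, sex, income status, fracture type, comorbidities, and emergency visits and hospitalizations in the prior year. Month, season and year of admission are not among them.
- **Section 3, Outcomes.** Outcomes are "assessed within 30 days postadmission". On the infections: "Postfracture infections were identified by physician-coded diagnoses during hospitalization or subsequent claims". The only further eligibility rule is: "Patients with pneumonia or septicemia within 6 months before the fracture were excluded".
- **Section 5, Statistical Analysis.** Adjusted ORs from logistic regression are to assess the effect of vaccination on infections and mortality. No season term or interaction is mentioned. The sensitivity analyses are "stratified by age, sex, comorbidity burden, and fracture type".

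Neither influenza season nor viral circulation is mentioned anywhere. The propensity covariates are referred to Table 1, which is not in the supplied text.

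**The concern.** Through influenza, a vaccine can lower pneumonia, septicemia, intensive care use or death only to the extent that the patient meets the virus during follow-up. With a year of follow-up, season would largely average out within each patient. With 30 days it does not: one patient's whole window may fall at peak circulation and another's when there is little. Because the outcomes have many causes, the second patient contributes events that the vaccine has less chance of preventing, yet carries the same weight.

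Two things are at stake. First, the all-year OR understates a true effect that is concentrated in season. Second, and more important in an observational comparison, a pooled OR cannot show whether the association rises and falls with influenza. A difference between vaccinated and nonvaccinated patients that the covariates miss would persist off-season; an effect acting through influenza should weaken. None of the four planned strata separates these explanations.

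**Working it through.** **Documented inputs.** 213,381 vaccinated + 348,185 nonvaccinated = 561,566, which agrees with the stated cohort. Matching is 1:1, so there are at most 213,381 pairs; the number achieved is not stated. The documents give no power calculation, event rate or in-season share, so there is no planned figure to reproduce. Everything below rests on stated assumptions.

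**1. Averaging of the true effect.** Let f be the share of nonvaccinated events that fall in season. Then

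pooled ratio = f × (in-season ratio) + (1 − f) × (off-season ratio).

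| In-season | Off-season | f = 0.25 | f = 0.50 |
|---|---|---|---|
| 0.70 | 1.00 | 0.175 + 0.750 = 0.925 | 0.350 + 0.500 = 0.850 |
| 0.80 | 1.00 | 0.200 + 0.750 = 0.950 | 0.400 + 0.500 = 0.900 |
| 0.90 | 1.00 | 0.225 + 0.750 = 0.975 | 0.450 + 0.500 = 0.950 |
| 0.80 | 0.95 | 0.200 + 0.7125 = 0.9125 | 0.400 + 0.475 = 0.875 |

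For an in-season ratio of 0.80, the part of the risk reduction lost is 1 − (1 − pooled)/0.20. That is 75% to 50% with an off-season ratio of 1.00, and 56% to 38% with 0.95. At f = 0.75 and an off-season ratio of 1.00, the pooled ratio is 0.60 + 0.25 = 0.85 and the loss is 25%.

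**2. The same on the odds scale.** Average the risks over the two seasons in each group, then take the ratio of the two odds. Assume 25% to 50% of admissions in season, an off-season control risk of 2% to 5%, an in-season risk 1.0 to 1.5 times that, and an off-season OR of 1. In-season ORs of 0.70, 0.80 and 0.90 pool to 0.82–0.93, 0.88–0.95 and 0.94–0.98. For example, with 25% in season, 5% risk throughout and an in-season OR of 0.80:

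- in-season vaccinated risk: odds 0.05263 × 0.80 = 0.04211, so risk 0.04040;
- pooled vaccinated risk: 0.25 × 0.04040 + 0.75 × 0.05 = 0.04760;
- pooled OR: (0.04760/0.95240)/0.05263 = 0.95.

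**3. Why the pooled OR cannot be interpreted alone.** Suppose residual differences multiply the OR by 0.85 in every month.

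- With no vaccine effect, the pooled OR is 0.85.
- With no residual differences but a true in-season OR of 0.70, half of admissions in season and equal risk in both seasons, the pooled OR is also 0.85.
- With residual differences of 0.85 and a true in-season OR of 0.80 (5% off-season risk), the pooled OR is 0.75 to 0.81, which is at or beyond the true in-season effect.

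Season strata separate the cases: 0.85 in both seasons in the first; 0.70 and 1.00 in the second; 0.80 × 0.85 = 0.68 in season and 0.85 off-season in the third.

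**4. Imbalance in season between the groups.** This is a smaller matter. With no vaccine effect, one third of admissions in season on average, a 5 to 10 percentage-point difference in that share between groups, and an in-season risk 1.2 to 1.5 times a 5% off-season risk, the OR moves only to 1.01–1.05.

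**5. Precision.** If the variance of the log OR is inversely proportional to events, the in-season interval widens by 1/√f: 1/√0.50 = 1.4 to 1/√0.25 = 2.0. The off-season interval widens by 1/√0.75 = 1.15 to 1/√0.50 = 1.4. The standard error of the interaction is √(1/f + 1/(1 − f)) times the pooled one: 2.0 at f = 0.50 and 2.3 at f = 0.25.

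**The case against.** The best defence is that section 2 asks for the association after fracture admission and names no season. An all-year OR answers that question, and it is diluted only relative to a different estimand. This stands: the planned OR is not invalid. But section 5 presents the ORs as measures of the effect of vaccination, and that reading needs more than the average.

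A reader might also infer several stronger things that the documents do not support.

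- *Off-season patients could not meet influenza.* The documents contain no circulation data. A lower chance is all the argument needs. Likewise, that admissions come from every month is inferred from the absence of a restriction.
- *Half to three quarters of the effect is lost.* That range follows only from an off-season ratio of exactly 1.0 and an assumed share of 25% to 50%. Step 1 shows losses of 38% to 56%, or 25%, under other reasonable values.
- *The reported OR will be too close to 1.* Averaging acts on the true effect. Step 3 shows that residual differences can carry the reported OR to or past the in-season effect.
- *The conclusion should rest on the in-season OR alone.* That OR may be confounded too: 0.68 rather than 0.80 in step 3. It has to be read against the off-season OR.

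Table 1 is not in the supplied text, so season may already be a propensity covariate. That would balance season between the groups, but it would neither separate the two effects nor undo the averaging.

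**Conclusion.** The point holds as a limit on what the study can conclude, not as an error in the planned estimate. The supplied text contains no restriction, listed matching variable, model term or stratum for admission season, although the window is 30 days and the outcomes are not specific to influenza.

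Whenever the true effect is weaker off-season, the all-year OR averages it toward 1. With an in-season ratio of 0.80 and 25% to 50% of events in season, the pooled ratio is 0.95 to 0.90 if the off-season ratio is 1.0, and about 0.91 to 0.875 if it is 0.95. The direction depends only on the off-season effect being weaker; the size depends on shares and ratios that the documents do not give. Where the reported OR will lie relative to the in-season effect cannot be said, because residual differences may act the other way. As written, the plan cannot distinguish these possibilities.

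**What to change.** 1. Keep the all-year OR and describe it as the average over admissions.
2. Define admission season in advance: whether or not the 30-day window overlaps influenza circulation, set year by year where surveillance data allow.
3. Add season to the stratified analyses in section 5. Report in-season and off-season ORs and a vaccination-by-season interaction for pneumonia, septicemia, intensive care use and mortality. The argument is not made here for urinary tract infection.
4. If Table 1 does not already include season and year of admission, add them to the propensity model or to the outcome regression.
5. State in advance how the off-season OR will be read: if it is about as far below 1 as the in-season OR, the association is not attributed to the vaccine.

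**Cost.** Season derives from the admission date already held, plus surveillance data where they are used. The text is in the past tense, so matching appears to be done. Adding season to the outcome regression avoids rerunning it; adding season to the propensity model does not.

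The in-season interval is about 1.4 to 2 times wider under the assumed shares, and the interaction is less precise still. The cohort can probably bear this. With one third of admissions in season and 50% to 100% of vaccinated patients matched, there are about 35,600 to 71,100 in-season pairs. At two-sided 0.05, 5% risk in both seasons, an in-season OR of 0.90 and no off-season effect, power is 85–99% in season against 40–67% pooled. At 2% risk it is 48–77% against 19–34%.

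One limit remains: if vaccination is itself seasonal, which the documents do not state, the interaction cannot fully separate influenza circulation from time since vaccination.

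### No measure of injury severity is named in the listed match or the stratified analyses, so a severity imbalance left after matching could confound intensive care use, and plausibly stay and cost.

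*Combined protocol and SAP*

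**What the plan says.** Section 2 (Study Design) builds the cohort from "561,566 patients aged ≥65 years" who were "admitted for fracture treatment between 2009 and 2020". The only clinical exclusion is in section 3 (Outcomes): "Patients with pneumonia or septicemia within 6 months before the fracture were excluded". Nothing in the text restricts entry by mechanism of injury, multiple injury or associated organ injury.

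Section 2 then calls for "1:1 propensity score matching (PSM"). Apart from age, sex and low-income status, the listed variables are "Fracture type and comorbidities (within 24 months") and "Emergency visits and hospitalizations during the prior year". Section 5 (Statistical Analysis) describes the propensity model as "including clinically relevant covariates (Table 1"). That table is not in the supplied text.

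Section 3 names seven primary outcomes within 30 days, among them "Intensive care use", length of stay, total expenditure and death. Section 5 specifies adjusted odds ratios for the infections and for mortality only. For intensive care use, stay and expenditure, only the general chi-square and t-test lines apply. The stratified analyses use age, sex, burden of comorbidity and type of fracture.

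**The concern.** Two patients with the same fracture type can have very different injuries: an isolated fracture from a fall, or the same fracture with head or chest trauma from a collision. The second patient is plausibly more likely to need intensive care, stay longer, cost more and die early, whatever the vaccination history.

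Comorbidities and prior-year use are measured before the injury, so they cannot describe how severe it was. Fracture type is the only listed variable that bears on the injury, and its categories are not defined. It is at best a partial proxy.

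Vaccination was not randomized, so balance on a variable outside the match cannot be presumed. For intensive care use, stay and expenditure, matching is the only stated protection. In a cohort of this size, a modest imbalance in severity could appear as a statistically clear vaccine association.

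**Working it through.** **The plan's own figures.** Section 2 gives 213,381 vaccinated and 348,185 unvaccinated patients. Their sum is 561,566, which matches the stated total. Matching 1:1 can keep at most 213,381 pairs, or 426,762 patients. The documents give no share of severe injury in either group and no outcome risks, so the size of any confounding cannot be estimated from them. What follows is an illustration.

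**Assumed inputs (none from the documents).**
- No true vaccine effect.
- Intensive care use 50% with severe injury and 5% without; as a variant, 30% and 5%.
- 30-day mortality 8% with severe injury and 2% without.
- Severe share *s* remaining after matching: 3% in one group, and 3%, 3.5%, 4% or 5% in the other.

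**Formula.** Risk in a group: p = low × (1 − s) + high × s. The spurious odds ratio is [p1/(1 − p1)] / [p0/(1 − p0)], with 1 for vaccinated and 0 for unvaccinated.

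**Intensive care, 3% vs 4%.**
- p1 = 0.05 × 0.97 + 0.50 × 0.03 = 0.0635
- p0 = 0.05 × 0.96 + 0.50 × 0.04 = 0.0680
- OR = (0.0635/0.9365) / (0.0680/0.9320) = 0.93

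**Death, 3% vs 4%.**
- p1 = 0.02 × 0.97 + 0.08 × 0.03 = 0.0218
- p0 = 0.02 × 0.96 + 0.08 × 0.04 = 0.0224
- OR = (0.0218/0.9782) / (0.0224/0.9776) = 0.97

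**Both directions.**

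| Severe share, vaccinated vs unvaccinated | Intensive care OR (50% vs 5%) | Intensive care OR (30% vs 5%) | Death OR (8% vs 2%) |
|---|---|---|---|
| 3% vs 3% | 1.00 | 1.00 | 1.00 |
| 3% vs 3.5% | 0.96 | 0.98 | 0.99 |
| 3% vs 4% | 0.93 | 0.96 | 0.97 |
| 3% vs 5% | 0.87 | 0.92 | 0.95 |
| 3.5% vs 3% | 1.04 | 1.02 | 1.01 |
| 4% vs 3% | 1.08 | 1.05 | 1.03 |
| 5% vs 3% | 1.15 | 1.09 | 1.06 |

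**Would it look significant?** Take the largest possible matched sample, 213,381 per group, and treat the groups as independent: z = (p0 − p1) / √{[p1(1 − p1) + p0(1 − p0)] / 213,381}. For 3% vs 4%:
- Intensive care, 50% vs 5%: 0.0045 / 0.000759 = 5.9
- Intensive care, 30% vs 5%: 0.0025 / 0.000720 = 3.5
- Death: 0.0006 / 0.000450 = 1.3

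Under these assumptions, a one-point imbalance would be expected to look significant for intensive care use but not for death. Nothing was computed for stay or expenditure, because the documents give no basis for their means or spread.

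**The case against.** The strongest reply is that pooling different severities does not bias anything. The illustration gives 1.00 whenever the shares are equal. Bias needs an imbalance that survives matching on age, sex, income, fracture type, comorbidity and prior use, and the documents show none. This stands, and it is why the point is conditional.

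A reader might also infer that any such bias favours vaccination, on the argument that people who skip preventive care take more risks. The documents do not support this. The opposite is equally untested: fitter, more mobile vaccinated people could have more exposure to traffic.

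Three further replies have some force.
- Section 2 says the matching variables included those listed, and Table 1 is unseen. If it contains severity variables, the call to add them to the score falls.
- Fracture type is both matched and stratified on. If its categories separate multiple or skull and rib fractures from isolated limb fractures, much of the severity mix is already handled. The supplied text does not say.
- Admission for fracture treatment may mean that the fracture led the admission, which could leave out patients admitted mainly for head or chest injury. That major trauma enters at all is inferred from the absence of an exclusion.

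These replies reduce the likely size of the problem. None supplies a control for severity that is visible in the text.

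**Conclusion.** The point holds in conditional form. The supplied text names no variable for the severity of the index injury in the match or the stratified analyses, so residual confounding by severity is possible and unaddressed. Intensive care use is most exposed. Stay and expenditure are plausibly exposed, but this is reasoned rather than calculated. Mortality is less exposed.

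For a one-point difference in severe share (3% and 4%), the spurious odds ratio for intensive care is 0.93 or 1.08 depending on direction (0.96 or 1.05 with the milder risk). For death it is 0.97 or 1.03. All of these rest on assumed risks and shares.

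Two stronger readings go beyond the documents. One is that these outcomes already partly compare how badly patients were injured; that needs a shown imbalance. The other is that leaving severity out costs important precision. With a 3% share and the assumed risks, severity explains about 0.5% of the variance in death (0.03 × 0.97 × 0.06² / 0.0213) and about 10% in intensive care use (0.03 × 0.97 × 0.45² / 0.0595). That is a standard-error gain of roughly 0.2% and 5%, which matters little in a cohort of this size.

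**What to change.** First check Table 1 and define the fracture-type categories in section 2. Unless Table 1 already includes them:

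1. Add to the propensity score, from the index-admission diagnoses, indicators for associated intracranial and thoraco-abdominal injury, the number of fracture sites, and transport-accident external cause where coded. Injury diagnoses describe the event that brought the patient in, so adjusting for them does not adjust away a vaccine effect.
2. Report the post-match standardized difference for each of these variables.
3. Add to section 5 a sensitivity analysis restricted to patients with an isolated fracture and none of these codes, covering intensive care use, stay, expenditure and mortality.

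The cost is a set of code lists applied to claims already held, a rerun of the match and one extra analysis. The downside is that external-cause coding in claims may be incomplete, so the associated-injury codes would have to carry most of the adjustment.

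### Pneumococcal vaccination is absent from the listed eligibility, matching and sensitivity variables, so part of its effect on pneumonia and septicemia could be credited to influenza vaccine

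*Combined protocol and SAP*

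**What the plan says.** - **Exposure (section 2).** The cohort is "561,566 patients aged ≥65 years" admitted for fracture. Those who "received IV within 12 months prior to admission, while" the comparison group had not are the two arms. No other vaccine enters the definition.
- **Matching (section 2).** The listed variables are "Demographics: age, sex", low-income status, fracture type, comorbidities over 24 months, and "Emergency visits and hospitalizations during the prior year". None is a vaccination or preventive-care item.
- **Eligibility (section 3).** The stated clinical exclusion is pneumonia or septicemia in the 6 months before the fracture.
- **Outcomes (section 3).** Pneumonia and septicemia are two of the seven primary outcomes.
- **Measures (section 4).** Definitions cover income status, comorbidities, infections and influenza vaccine types. No other vaccine is defined.
- **Analysis (section 5).** The propensity model takes its covariates from Table 1, which is not in the available text. The covariates of the adjusted outcome model are not listed. The sensitivity analyses are "stratified by age, sex, comorbidity burden, and fracture type". The odds ratios are described as measuring influenza-vaccine effects.

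**The concern.** Pneumococcal vaccine is aimed at pneumonia and invasive infection in the age group studied, and it is plausible that people who accept one vaccine more often accept the other. Both statements are general knowledge; the documents give no figure for either. If they hold here, the arms may differ in a second preventive exposure that acts on two primary outcomes.

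Matching on illness and acute-care use balances this exposure only as far as those variables predict its uptake. The planned stratified analyses would not reveal it, because the same imbalance could recur in every stratum. At stake is the attribution of a modest protective odds ratio for pneumonia or septicemia in a study large enough to declare a few percent significant.

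**Working it through.** **1. The plan's own figure.** 213,381 + 348,185 = 561,566, which agrees with section 2; 213,381 / 561,566 = 38.0% vaccinated. With 1:1 matching there can be at most 213,381 pairs. The plan states no outcome rates, effect size or power.

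**2. Assumed inputs (none in the documents).** Pneumococcal coverage, read as coverage remaining after matching: pv = 20–40% in influenza vaccinees and pu = 10–15% in nonvaccinees. Risk ratio of pneumococcal vaccine for the outcome: R = 0.7–0.9. Outcome risk: 3%.

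**3. Spurious risk ratio when influenza vaccine does nothing.** For an unmeasured binary confounder,

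B = [1 − pv(1 − R)] / [1 − pu(1 − R)].

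| pv | pu | R | B |
|---|---|---|---|
| 20% | 15% | 0.9 | 0.980/0.985 = 0.995 |
| 20% | 10% | 0.9 | 0.980/0.990 = 0.990 |
| 40% | 15% | 0.9 | 0.960/0.985 = 0.975 |
| 40% | 10% | 0.9 | 0.960/0.990 = 0.970 |
| 20% | 15% | 0.7 | 0.940/0.955 = 0.984 |
| 20% | 10% | 0.7 | 0.940/0.970 = 0.969 |
| 40% | 15% | 0.7 | 0.880/0.955 = 0.921 |
| 40% | 10% | 0.7 | 0.880/0.970 = 0.907 |
| 30% | 10% | 0.8 (central) | 0.940/0.980 = 0.959 |

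The range is 0.907 to 0.995. If pv = pu, B = 1 and there is no bias. At 3% risk the odds ratio is close to the risk ratio: in the central case the risks are 0.0282 and 0.0294, and the odds ratio is (0.0282/0.9718)/(0.0294/0.9706) = 0.958.

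**4. Precision.** Treating the arms as independent, the half-width on the log risk ratio is 1.96 × √[2(1 − p)/(np)]. With n = 213,381 and p = 0.03 this is 1.96 × √(1.94/6,401) = 1.96 × 0.0174 = 0.034. With n = 100,000 it is 1.96 × √(1.94/3,000) = 0.050.

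**5. Bias against precision.** At the maximum match, a spurious ratio exceeds the half-width when it falls below exp(−0.034) = 0.967. The chance of a two-sided p < 0.05 with no influenza-vaccine effect is about Φ(|ln B|/0.0174 − 1.96), plus a small opposite tail:

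- Mild end, B = 0.995: |ln B| = 0.005, chance about 6%, barely above nominal.
- Central, B = 0.959: |ln B| = 0.042, chance about 67%. With 100,000 pairs it is about 37%.
- Strong end, B = 0.907: |ln B| = 0.097, chance above 99%.

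**6. Could it explain a large effect?** Going beyond the range in step 2 to 60% vs 10% coverage with R = 0.7 gives 0.82/0.97 = 0.845. Even that contrast does not produce a large reduction.

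**The case against.** The strongest objection is that the omission cannot be proved. Section 2 introduces its list in a way that need not be exhaustive, section 5 defers to Table 1, and the outcome model's covariates are not given. This stands: a reader might infer that the plan definitely leaves the variable out, and the documents do not support that. What can be said is that it is missing from every list in the text, and that section 4 defines no such variable.

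Second, co-uptake and vaccine effect come from outside the documents. Matching on age, income, comorbidity and prior care may narrow the uptake difference, and with equal uptake the bias is nil. This also stands, and it is why the result is given as a range. It does not remove the point, because only measuring uptake can show that it is balanced.

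Third, the bias is small. A reader might infer that no protective odds ratio for pneumonia or septicemia could be attributed to influenza vaccine. The arithmetic does not support that: only the part due to a residual uptake difference transfers, and under these assumptions it is at most about 9%. Significance is not assured either. It depends on an assumed outcome risk and on a pair count that is a ceiling, and at the mild end the bias would rarely be noticed.

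Last, section 2 frames the aim as an association, which softens the claim. Section 5, however, uses the language of effects.

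**Conclusion.** The point holds as a conditional one and is worth acting on. On the lists in sections 2 to 5, a plausible confounder of two of the seven primary outcomes is not accounted for. With no influenza-vaccine effect, the spurious risk ratio is about 0.91 to 0.995 (0.96 centrally), assuming coverage of 20–40% vs 10–15% after matching and a risk ratio of 0.7–0.9. Against a half-width of about 0.034 (at most 213,381 pairs, 3% risk), the middle and stronger part of that range could be reported as significant, while the mild end usually would not. It matters for a near-null or modest result and would not account for a large one. Nothing here reaches the other five primary outcomes directly. If Table 1 already contains pneumococcal vaccination, the point falls, apart from naming the variable in section 2.

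**What to change.** **If pneumococcal vaccination records are in, or can be linked to, the claims** (the documents do not show whether they are):

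- Add receipt before admission (yes/no) to the propensity model and name it among the matching variables in section 2. Use one look-back window for all admission years from 2009 to 2020, so that ascertainment does not drift with calendar time.
- Report its balance after matching.
- Add a sensitivity analysis restricted to patients with no recorded pneumococcal vaccination, re-matched within that subset so that pairs are not broken.

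**If records are not available:** name it as an unmeasured confounder. Report a quantitative bias analysis (external adjustment as above, or an E-value). In section 5, replace the effect wording for pneumonia and septicemia with an association that may include pneumococcal co-vaccination.

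**Cost.** With records: a rerun of the match, a few more unmatched patients and a smaller restricted sample, plus the linkage work if the records lie outside the claims. Without records: a short bias analysis and a change of wording.
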